## DEFINITION OF TERMS

Monitoring Phase	A subject who experiences a $\geq 50\%$ decrease in sperm concentration, and/or motility, and/or morphology at any time after 13 weeks will start the Monitoring Phase. Semen samples will be collected every 13 weeks starting from their entry into the Monitoring Phase, for up to 52 weeks or until Reversibility is met, whichever is achieved first.
Arthritis Responder	For RA, PsA, AS or nrAxSpA - improvement in physician's global assessment (PhGADA) of at least 20% compared to Baseline (Day 1) at the specified assessment time
Arthritis Non-responder	For RA, PsA, AS or nrAxSpA, a subject who does not fulfill the definition of Arthritis Responder at the specified assessment time point (refer to Appendix 2 )
Pre-specified decrease threshold	A $\geq 50\%$ decrease in sperm concentration, and/or motility, and/or morphology in comparison to Baseline (Screening). The mean of values for each of the sperm parameters (measured from 2 separate semen samples) will be used in all analyses. Samples will be collected within a 14-day period and with an ejaculation-free period of $\geq 48$ hours and $\leq 7$ days.
Reversibility	Reversibility is met when all semen parameter(s) qualifying the subject to enter into the Monitoring Phase return(s) to greater than 50% of Baseline (ie, to greater than $[0.50 \times \text{mean of 2 sperm collections collected at the Screening visit (ie, Baseline)}]$ ).
Week 13	The Week 13 Study Visit occurs once a subject completes 13 weeks of blinded study drug, and is inclusive of all study assessments performed at the clinic visit and the semen sample collection visits associated with this time point.
Week 26	The Week 26 Study Visit occurs once a subject completes 13 weeks of open-label filgotinib or Standard of Care treatment during the Extension Phase, and is inclusive of all study assessments performed at the clinic visit and the semen sample collection visits associated with this time point.
Standard of Care	Locally approved treatment, accepted by medical experts as a proper treatment for rheumatic conditions, prescribed according to best clinical practice, with no known testicular toxicity. Standard of Care will be reimbursed by the sponsor until the Week 156 visit of the Extension Phase or until a subject completes the Monitoring Phase.

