### 3.1. Double-blind Treatment Phase (Day 1 through Week 13 Study Visit)

Figure 3-2. Double-blind Treatment Phase – Week 13 Evaluation

[figure not shown]

During the Double-blind Treatment Phase, all subjects will receive blinded study drug for 13 weeks starting from the Day 1/Randomization Study Visit. Subjects will visit the clinical study center to be evaluated for clinical and laboratory assessments at Day 1, Week 2, Week 4, Week 8, and Week 13. At the Week 13 study visit, sperm parameters (see Semen collection and Analysis) will be evaluated to determine whether they meet any of the pre-specified decrease thresholds (see [Definition of Terms](#)). In addition, arthritis response status (Arthritis Non-responder vs Arthritis Responder, see [Definition of Terms](#)) will be determined. As soon as the Week 13 semen results are available to the investigator and have been evaluated, subjects are assigned to one of the following:

- Subjects whose semen parameters meet any of the pre-specified decrease thresholds, regardless of arthritis response status, will discontinue blinded study drug and enter the Monitoring Phase. These subjects will also have a safety follow-up visit 30 days after last study drug dose.
- Subjects who are arthritis Non-responders and whose sperm parameters do not meet any of the pre-specified decrease thresholds will discontinue blinded study drug and start Standard of Care treatment (see [Definition of Terms](#)) during the Extension Phase. These subjects will also have a safety follow-up visit 30 days after last study drug dose.
- Subjects who are Arthritis Responders and whose sperm parameters do not meet any of the pre-specified decrease thresholds will be unblinded by the IWRS system and enter the Extension Phase. Subjects on filgotinib will convert to open-label filgotinib and subjects receiving placebo will switch to Standard of Care treatment.

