### **6.4. Double-blind Treatment Phase (Day 1 Through Week 13 Study Visit)**

All subjects will receive blinded study drug until completion of all Week 13 assessments.

Study assessments will be completed as specified in the Study Procedures Table ([Appendix 2](#)).

Invasive study procedures such as blood draws should be done at the end of a study visit, as much as possible.

The end of the Double-Blind Treatment Phase is when the Week 13 semen results are available to the investigator and have been evaluated. Based on this evaluation, subjects are assigned to enter the Monitoring Phase or the Extension Phase.

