1.3. Sample Size and Power

Results of this study will be pooled with the results of a separate study being conducted in subjects with inflammatory bowel disease (GS-US-418-4279 [MANTA]) with the same objectives. The total planned number of subjects in both studies combined will be up to approximately 250 subjects.

A sample size of approximately 100 evaluable subjects per group (ie, 100 subjects in the filgotinib 200 mg group and 100 subjects in the placebo group) is adequate for the purposes of estimating cumulative distribution curves and producing a 95% confidence interval (CI) width that is reasonably narrow for the proportion of subjects in each group who experience a $\geq 50\%$ decrease in sperm concentration compared to baseline. An evaluable subject is defined as a subject with 2 semen samples at both baseline and at Week 13 that are eligible for mean calculation for sperm concentration with visit window assignment for the mean calculation based on the date of the first of 2 evaluable sample collections. This 200 subject sample size is suggested in FDA's guidance on testicular toxicity studies {U. S. Department of Health and Human Services (DHHS) 2018}. Assuming a 20% rate of non-evaluable subjects at Week 13, up to 250 subjects may be enrolled to obtain 200 evaluable subjects.

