3.7. Analysis Visit Windows

3.7.1. Definition of Study Day

The First Dosing Date of Double-Blind Filgotinib/Placebo is defined as the date when subjects take their first dose of double-blind filgotinib/placebo as recorded on the Study Drug Administration eCRF.

The Last Dosing Date of Double-Blind Filgotinib/Placebo is defined as the date when subjects take their last dose of double-blind filgotinib/placebo as recorded in the Study Drug Administration eCRF.

The Last Dosing Date of Any Filgotinib is defined as the date when a subject takes their last dose of double-blind or open-label filgotinib as recorded in the Study Drug Administration eCRF.

The Start Date of Extension Phase is defined as the first dose date of open-label filgotinib (for rheumatic disease responders randomized to filgotinib who continued on open-label filgotinib in extension phase) from the study drug administration eCRF or last dose date of double-blind study drug +1 day for subjects who have a non-missing standard of care start date in the extension phase of the study. In some countries, it takes time to obtain a new standard of care drug for rheumatic disease when subjects undergo a medication switch (especially for biologics), so the “standard of care” is to continue background medications alone or in rare cases, to take no rheumatic disease medication until the new regimen is available.

The End Date of Extension Phase is defined as last dose date of open-label filgotinib as recorded on the Study Drug Administration eCRF for subjects on open-label filgotinib in the Extension Phase. The end date for standard of care in extension phase will be 1 day prior to the date the subject went into the Monitoring Phase (ie, date the site was notified of subject meeting a prespecified sperm decrease threshold). Subjects who do not participate in Monitoring Phase but have a Study Completion eCRF that states that the subject has either completed study or prematurely discontinued study will have the last date of standard of care estimated using the last of the following dates: last Covance lab date, last eCRF visit date, date of last sperm sample collection, and death date (if subject died).

Study Day will be calculated from the first dosing date of double-blind filgotinib/placebo and derived as follows:

- For postdose study days: Assessment Date – On-Filgotinib/Placebo Study Day 1 + 1
- For days prior to the first dose: Assessment Date – On-Filgotinib/Placebo Study Day 1

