Table 3-4. Analysis Visit Windows for On-Treatment Semen Parameters

Analysis Visit	Nominal Day (Study Day)	Lower Limit (Study Day)	Upper Limit (Study Day)
Baseline	1	None	1
Week 13	92	85	112
Week 26	183	170	260
Week 39	274	261	351
Week 52	365	352	442
Week 65	456	443	533
Week 78	547	534	624
Week 91	638	625	715
Week 104	729	716	806
Week 117	820	807	897
Week 130	911	898	988
Week 143	1002	989	1079
Week 156	1093	1080	≥ 1093

Note: Primary analysis includes data up to first dose date of open-label filgotinib/first date in extension phase (if non-missing) or to last dose date of double-blind drug + 7 days (for those not continuing in Extension Phase).

Secondary analysis includes all “on-treatment” data up to the last dose date in extension phase (if non-missing) or to last dose date of any study drug + 7 days.

**Table 3-5. Analysis Visit Windows for Semen Parameters in Monitoring Phase
(Calculated from Last Dose Date of Any Study Drug/End of Extension Phase for those on Standard of Care in Extension Phase)**

Analysis Visit	Nominal Day (FU Day)	Lower Limit (FU Day)	Upper Limit (FU Day)
MP Week 13	91	8	104
MP Week 26	182	105	195
MP Week 39	273	196	286
MP Week 52	364	287	377

MP = Monitoring Phase; FU = Follow-Up.

NOTE: All visit windows for monitoring phase will be calculated from last dose date of any study drug/end date in Extension Phase (date site receives confirmation of subject meeting sperm parameter decrease threshold) for subjects taking standard of care in extension phase who met pre-specified sperm decrease thresholds.

FU Day = visit date – last dose date of any study drug/last date in extension phase.

Investigator Assessment of Electrocardiogram (ECG) Visit Assignment

Nominal visits from the clinical database will be used to assign timepoints for the investigator's assessment of ECG. Baseline will use the nominal visit "Screening"; Week 13 or Early Termination will use a nominal visit of "Week 13" or "Early termination" if subject prematurely discontinued double-blind study drug; and LTE Week 156 or Early termination visit for subjects in the filgotinib 200 mg to open-label filgotinib 200 mg group will use nominal visits of "Extension Week 156" or "Early termination" for subjects who early terminated after starting open-label filgotinib (per protocol Amendment 1 subjects taking standard of care in extension phase are no longer required to complete an ECG at Week 156 or early termination).

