6.2. Primary Analysis of Primary and Secondary Endpoints

The primary analysis will be an observed cases analysis at Week 13 while subjects are on double-blind study drug as described in FDA's guidance for industry on testicular toxicity studies [{U. S. Department of Health and Human Services \(DHHS\) 2018}](#).

The main estimators of a While on Treatment Strategy estimand will be utilized for the primary analysis of primary and secondary endpoints at Week 13:

BINARY ENDPOINT	WHILE ON-TREATMENT STRATEGY
Population	Semen Analysis Set (subjects with 2 evaluable semen samples collected at baseline and at the Week 13 analysis visit) as defined in Section 3.1.2 of this SAP.
Patient Level Outcome to be Measured	Binary outcome for a subject meeting a $\geq 50\%$ decrease from baseline in sperm concentration at Week 13. Outcome is determined based on the mean of 2 evaluable semen samples at a visit.
Measure of intervention effect and handling of intercurrent events	Measure of treatment effect assuming that the treatment effect prior to the intercurrent event of treatment early discontinuation is of interest. Data included to last dose date double-blind drug + 7 days will be considered "while on-treatment" for those who permanently discontinue double-blind study drug and do not continue to Extension Phase.
Population level summary measure	Difference in a binary outcome, comparing those assigned to filgotinib versus those assigned to placebo.
Estimators	
Main estimator: A stratified Mantel-Haenszel test (stratification factor: sperm concentration [15 – 50 M/mL, > 50 M/mL], concurrent MTX use [yes, no]) will be used to estimate the difference in proportions (filgotinib – placebo) and corresponding 95% CI {Koch 1989}. Calculation for difference in proportions and 95% CI provided in Appendix 2.
 
Note: When performing the stratified Mantel-Haenszel test, the 15 – 25 and > 25 – 50 M/mL strata for sperm concentration will be combined (eg, 15 – 50 M/mL) due to the small number of subjects in the lowest stratum; disease type will not be included as a stratification factor due to the small number of subjects with RA.

CONTINUOUS ENDPOINTS	WHILE ON TREATMENT STRATEGY
Population	Semen Analysis Set (subjects with 2 evaluable semen samples collected at baseline and at the Week 13 analysis visit) as defined in Section 3.1.2 of this SAP.

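### The primary Week 13 semen cut-off depends on the phase entered next, so a pair taken 2 to 7 days after the last blinded dose is kept for decliners and filgotinib responders but lost for non-decliners going to Standard of Care

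*SAP*

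**What the plan says.** The note under SAP Table 3-4 sets the data limit: "Primary analysis includes data up to first dose date of open-label filgotinib/first date in extension phase (if non-missing) or to last dose date of double-blind" treatment plus 7 days, the last part for subjects who do not go on to the Extension Phase. The estimand table in SAP 6.2 repeats the 7-day allowance "for those who permanently discontinue double-blind study drug and do not continue to Extension Phase".

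SAP 3.7.1 defines the start of the Extension Phase. For open-label filgotinib it is the actual first open-label dose. For Standard of Care it is derived: "last dose date of double-blind study drug +1 day for subjects who have a non-missing standard of care start date".

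Protocol 3.1 sets the route. A decliner (a fall of at least 50% in concentration, motility or morphology) goes to the Monitoring Phase. A non-decliner who is an arthritis non-responder goes to Standard of Care, whichever the arm. For responders who are non-decliners, "Subjects on filgotinib will convert to open-label filgotinib and subjects receiving placebo will switch to Standard of Care treatment".

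The protocol also keeps subjects on treatment. Section 6.4 says: "All subjects will receive blinded study drug until completion of all Week 13 assessments". The Week 13 definition takes in "all study assessments performed at the clinic visit and the semen sample collection visits associated with this time point". Protocol 3.1 says: "As soon as the Week 13 semen results are available to the investigator and have been evaluated, subjects are assigned".

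For dating a pair, SAP 1.3 uses "visit window assignment for the mean calculation based on the date of the first of 2 evaluable sample collections"; SAP 3.7.3 and 6.2 agree. All three are written for visit windows. None says whether the data cut-off follows the same rule.

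**The concern.** The Week 13 semen result supplies the primary endpoint and also decides the next phase. The next phase then decides how many days after the last blinded dose a sample still counts. So whether a subject enters the primary analysis can depend on that subject's own outcome and, among non-decliners, on arm.

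The 1-day limit for Standard of Care is not a guard against contamination by new treatment. SAP 3.7.1 itself notes that a new drug can take time to obtain, so the derived date can precede any real change. The same day off drug counts as on treatment for a decliner and not for a non-decliner.

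Losing non-decliners raises the observed proportion of decliners. If more are lost on placebo, filgotinib minus placebo moves down, which is the unfavourable direction in a testicular safety study.

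**Working it through.** **Design figure.** The SAP gives no power, event rate or margin. Its one sample-size sum is reproduced and not disputed: 200 / (1 - 0.20) = 250.

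**Step 1: apply the rule by route.** The pair is dated by its first sample, lies within Day 85 to 112, and the limit date is included.

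| Days from last blinded dose to first sample | Not entering Extension (all Week 13 decliners) | Filgotinib responder, non-decliner | Non-decliner going to Standard of Care |
|---|---|---|---|
| 0 to 1 | kept | kept | kept |
| 2 to 7 | kept | kept | lost |
| 8 or more | lost | kept if before first open-label dose | lost |

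- The responder column rests on protocol 3.1 and 5.1.2: unblinding and open-label dosing come only after the Week 13 semen results are known.
- If the limit date is excluded, the Standard of Care route loses day 1 as well.
- A lost pair cannot count at Week 26, because that window opens at Day 170.
- If the cut-off applied to each sample, more pairs would be exposed. Protocol 6.11 requires at least 48 hours of abstinence before each sample, so a second sample is at least 2 days after the first.

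**Step 2: can it happen?** Not if protocol 6.4 is followed. Other text leaves room. Protocol 3.4 and 6.11 list the collection as after the Double-blind Treatment Phase. The procedures table (protocol Appendix 2) allows samples after the visit day, and its Week 13 dispensing is for open-label filgotinib only, with no blinded resupply. These passages should be reconciled with 6.4.

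**Step 3: effect per subject.** With x decliners among n placebo subjects, losing one non-decliner adds x/(n-1) - x/n.

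- n = 100: x = 5 gives 0.05 points; x = 10 gives 0.10.
- n = 50: x = 2.5 gives 0.10 points; x = 5 gives 0.20.

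SAP 1.3 plans about 100 evaluable per group and up to about 250 subjects over two studies. This study's share is not stated, so 50 per arm is an assumption.

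**Step 4: effect on the difference.** All inputs are assumptions:

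- p: true rate, equal in both arms
- f: share of Standard of Care-bound non-decliners with a first sample on days 2 to 7
- r: filgotinib responder share, none of whose pairs are lost
- q: share of subjects without a concentration event who get the 7-day limit anyway (motility or morphology decliners, or no Extension Phase)

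Placebo = p / [p + (1-p)(1 - (1-q)f)]

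Filgotinib = p / [p + (1-p)(1 - (1-q)(1-r)f)]

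| p | f | r | q | Filgotinib | Placebo | Difference (points) |
|---|---|---|---|---|---|---|
| 0.05 | 0.05 | 0.5 | 0.2 | 5.10% | 5.20% | -0.10 |
| 0.08 | 0.05 | 0.6 | 0.1 | 8.13% | 8.35% | -0.21 |
| 0.08 | 0.10 | 0.6 | 0.1 | 8.27% | 8.72% | -0.45 |
| 0.10 | 0.10 | 0.7 | 0.1 | 10.25% | 10.88% | -0.63 |

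The true difference is 0 in every row. With f = 0 the shift is 0.

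**Step 5: compare with sampling error.** Unstratified half-width = 1.96 × sqrt(2p(1-p)/n). At n = 100 it is 6.0 points (p = 5%) and 8.3 (p = 10%); at n = 50 it is 8.5 and 11.8. With the SAP Appendix 2 standard error and four equal strata it is 7.1 and 9.0, then 11.3 and 13.7.

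**The case against.** **Protocol adherence.** Under 6.4 an Extension entrant gives both samples before the last blinded dose, and SAP 6.2 ties the 7-day allowance to early discontinuation. The allowance is therefore no evidence that Extension entrants give late samples. This stands: with full adherence the effect is nil.

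**Direction.** If open-label filgotinib began the day after the last blinded dose, responders would also be cut at plus 1 day and both arms would lose non-decliners alike. A true difference of 0 would stay 0, and a real one would be slightly inflated: 15% against 10% with f = 10% and q = 0 becomes 0.15/0.915 = 16.4% against 0.10/0.91 = 11.0%, or +5.4 points. This largely fails, because protocol 3.1 and 5.1.2 place open-label dosing after the semen results are known. But the size in the working does assume that no responder pair is lost.

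**Mitigations.** Protocol 8.5.1 promises sensitivity analyses for missing data patterns, and the SAP includes a multiple-imputation estimator. The Table 3-4 note admits extension-phase data to the secondary analysis. SAP 3.1 lists exclusion reasons, and protocol 8.3 summarizes missingness by arm and stratum. These may recover or reveal part of the loss, though neither summary is split by decline status. SAP 3.1.2 and the text between the end of 6.2 and 6.5 (apart from the last row of the imputation table) were not available for this check.

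**Stronger readings.** A reader might infer that the rule hides a testicular signal, or that subjects will certainly be lost. The documents support neither: the protocol provides for dosing through sampling, and the computed shift is a small fraction of sampling error.

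**Conclusion.** The inconsistency is real on the face of the SAP: within days 2 to 7, inclusion in the primary analysis depends on outcome and, through routing, on arm. Its effect is nil under protocol 6.4. Otherwise its frequency is unknown. With 5 to 10% of Standard of Care-bound non-decliners affected, filgotinib minus placebo shifts by about -0.1 to -0.6 points, against an unstratified half-width of about 6 to 12. That range assumes equal true rates of 5 to 10%, a responder share of 50 to 70%, q of 10 to 20%, and no responder pairs lost. This is a cheap improvement, not a threat to the primary conclusion. Confidence is medium, because parts of the SAP could not be checked.

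**What to change.** Use one cut-off for all routes in the Table 3-4 note and the SAP 6.2 table: last double-blind dose plus 7 days, applied to the first sample of the pair, within Day 85 to 112. Do not use the derived Extension start date for this purpose. The loss on days 2 to 7 then no longer differs by route.

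Make this the primary rule only if it is changed before unblinding. Otherwise report it as a labelled sensitivity analysis beside the current rule and document it in the CSR, as SAP section 1 provides. The SAP was signed in January 2021, and protocol Amendment 2 describes most assignments as already unblinded, so the sensitivity route is the one that fits now.

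In either case, report by arm and decline status how many subjects the current rule excludes. Flag any sample taken after the actual start of open-label filgotinib or Standard of Care.

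The cost is two sentences, one count and one extra run, with no new data. The downside is that a pair may span 14 days, so a second sample could fall up to 7 + 14 = 21 days after the last blinded dose and reflect the next treatment. The SAP's first-sample dating would already allow this for decliners if it governs the cut-off.

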## 6.11. Semen Collection Procedure

At each of the following time points, subjects will provide 2 separate semen samples collected within a 14-day period. Each semen sample must be collected with a  $\geq 48$  hours and  $\leq 7$  days ejaculation free period at the following time points.

- Screening (Baseline)
- After the Double-blind Treatment Phase (Week 13 study visit)
- Every 13 weeks during the Extension Phase
- Every 13 weeks during the Monitoring Phase
- At the Early Termination Visit

[figure not shown]
The 2 time-points for the semen sample collection will be scheduled in agreement with the investigator on the study visit day and/or as soon as possible after the visit day.

All decisions of retesting any semen/sperm parameter (i.e. obtaining a third sample at any of the above time points), must be approved by the Sponsor Medical Leader or designee before the retest. Such inquiries will only be considered in select instances where the semen sample with the questioned value(s) is found to be non-assessable or invalid (e.g. collection without adherence to ejaculation-free period; intercurrent illness or dehydration at time of collection; incomplete capture of semen sample; and/or sample processing or semen analysis that deviates from standardized procedure). The third semen sample, when indicated, must be collected within 14 days of the prior sample and with an ejaculation free period of  $\geq 48$  hours and  $\leq 7$  days (See [Figure 6-1](#)).

At each time point, the mean of 2 separate semen samples for each parameter will be used for the assessment of study eligibility, entry into the Extension Phase, entry into the Monitoring Phase, and exit from the Monitoring Phase.

The results of the semen analysis will be evaluated and discussed with the subject and he will be informed about the appropriate next steps to be taken in the study.

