FU-4*	Last Dose Date OL filgotinib (filgo to OL filgo); last dose date DB drug*, otherwise + 30 Days	Last Dose Date OL filgotinib (filgo to OL filgo); last dose date DB drug*, otherwise + 8 Days	Last Dose Date OL filgotinib (filgo to OL filgo); last dose date DB drug*, otherwise + 35 Days

Note: Data will be included for “on-treatment” visits up to the last dose date of standard of care in the extension phase (if non-missing) or up to last dose date of any study drug + 7 days.

*FU-4 visit collected based on days from last dose of open-label filgotinib (filgotinib 200 mg to OL filgotinib); EXT days for all (prior to Amendment 1) subjects / only non-responders (after Amendment 1) who switched to standard of care in extension phase; and from last dose date of double-blind study drug for those meeting sperm decrease threshold at Week 13 or prematurely discontinued in/at end of double-blind phase. Protocol specified an upper bound of + 5 days. FU-4 visit window is applicable for hematology, chemistry, vitals, and weight.

Table 3-3. Analysis Visit Windows for LH, FSH, Inhibin B, and Total Testosterone

Analysis Visit	Nominal Day (Study Day)	Lower Limit (Study Day)	Upper Limit (Study Day)
Baseline	1	None	1
Week 4	29	2	84
Week 13	92	85	112
Week 26	183	170	260
Week 39	274	261	351
Week 52	365	352	442
Week 65	456	443	533
Week 78	547	534	624
Week 91	638	625	715
Week 104	729	716	806
Week 117	820	807	897
Week 130	911	898	988
Week 143	1002	989	1079
Week 156	1093	1080	≥ 1093
FU-4*	Last Dose Date OL filgotinib (filgo to OL filgo); last dose date DB drug*, otherwise + 30 Days	Last Dose Date OL filgotinib (filgo to OL filgo); last dose date DB drug*, otherwise + 8 Days	Last Dose Date OL filgotinib (filgo to OL filgo); last dose date DB drug*, otherwise + 35 Days

Note: Data will be included for “on-treatment” visits up to the last dose date of standard of care in the extension phase (if non-missing) or up to last dose date of any study drug + 7 days.

*FU-4 visit collected based on days from last dose of open-label filgotinib (filgotinib 200 mg to OL filgotinib); off study drug but in EXT phase for all (prior to Amendment 1) subjects / only non-responders (after Amendment 1) who switched to standard of care in extension phase; and from last dose date of double-blind study drug for those meeting sperm decrease threshold at Week 13 or prematurely discontinued in/at end of double-blind phase. Protocol specified an upper bound of + 5 days.

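### The SAP Table 3-4 note, read literally, ends open-label filgotinib semen data on the last dose; this conflicts with its parallel notes and can drop end-of-phase pairs from one sequence

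*SAP*

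**What the plan says.** - **Cut-off for secondary semen data (SAP 3.7.2, note to Table 3-4).** On-treatment data are kept as "data up to the last dose date in extension phase (if non-missing) or to last dose date of any study drug + 7 days". The first branch is not limited to any treatment.
- **Same cut-off for laboratory tests, vital signs and hormones (notes to Tables 3-2 and 3-3).** Data are kept "up to the last dose date of standard of care in the extension phase (if non-missing"); failing that, the limit is 7 days after the final dose of any study drug. Here the first branch names Standard of Care.
- **Extension end date, open-label filgotinib (SAP 3.7.1).** "The End Date of Extension Phase is defined as last dose date of open-label filgotinib as recorded on the Study Drug Administration eCRF".
- **Extension end date, Standard of Care (SAP 3.7.1).** For men who complete or leave the study without entering Monitoring, it is the latest of several dates, one of which is the "date of last sperm sample collection". For men who enter Monitoring, it "will be 1 day prior to the date the subject went into the Monitoring Phase".
- **Monitoring Phase semen windows (SAP Table 3-5).** The first window opens at follow-up Day 8.
- **Collection (Protocol 6.11).** Two samples are taken within 14 days, each after at least 48 hours without ejaculation. They are scheduled "on the study visit day and/or as soon as possible after the visit day".
- **Dating a pair (SAP 3.7.3).** Two evaluable samples are needed, and the earlier one fixes the analysis window. The SAP does not say which sample is tested against the cut-off.

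**The concern.** The semen note is the only one of the three that leaves out the Standard of Care restriction, and semen is the main outcome of this trial. An open-label filgotinib man always has a non-missing extension dose date. Taken at its word, the note puts him in the first branch, and he never reaches the 7-day allowance that he receives for hormones at the same visit. Samples on follow-up Days 1 to 7 would then belong to neither semen table.

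Collection happens on or after the visit day and needs two samples, so the exposed pairs are those at the end of dosing: Week 156 and Early Termination. The Standard of Care end date moves out to the last sperm collection for men who do not enter Monitoring, so their last pair is retained. The by-sequence displays in SAP 6.5 could therefore lose end-of-phase pairs from the sequence with the longest filgotinib exposure and keep them in the other two. A man whose Week 156 pair shows a decrease could be counted in the reversibility table (SAP 6.6.2) and be missing from that visit's proportion (SAP 6.5.2 and 6.5.3).

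**Working it through.** The plan gives no figure to reproduce here. The check applies the SAP date rules to permitted collection dates.

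**Step 1: does the visit window remove the pair?** No. The Week 156 window in Table 3-4 runs from Day 1080 with an open upper end. Only the cut-off can remove a late final pair. The nominal Week 156 semen day is 1093, and full filgotinib exposure in SAP 4.2.1 is Day 1092 (156 × 7), so on nominal dates the final pair begins 1093 − 1092 = 1 day after full exposure. Day 1092 is an exposure category, not a stop date, so dosing has to be varied.

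**Step 2: inputs.** Days are counted from the visit (Day 0).
- First sample, s1: 0 to 7 (assumption; Protocol 6.11 says only on the visit day or as soon as possible after it).
- Gap to the second sample, g: 2 to 14 (48-hour minimum; 14-day collection period).
- Combinations: 8 × 13 = 104.
- Last open-label dose, L: −14 to +14 (assumption; the documents do not give its timing relative to Week 156 sampling).

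**Step 3: rules.**
- Literal note: keep if s1 ≤ L (first sample decides) or s1 + g ≤ L (both must qualify).
- Rule of Tables 3-2 and 3-3: replace L by L + 7.
- Standard of Care without Monitoring: the end date is never earlier than the last collection, so every pair is kept.

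**Step 4: example, L = 0.**
- Literal, first sample: s1 = 0 only, 1 × 13 = 13.
- Literal, both: s1 + g ≤ 0 is impossible because g ≥ 2, so 0.
- +7 days, first sample: s1 ≤ 7, 8 × 13 = 104.
- +7 days, both: s1 + g ≤ 7, 6 + 5 + 4 + 3 + 2 + 1 = 21.

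**Step 5: results (combinations kept, of 104).**

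| Last dose relative to visit | Literal, first sample | Literal, both | +7 days, first sample | +7 days, both | Standard of Care, no Monitoring |
|---|---|---|---|---|---|
| 14 days before | 0 | 0 | 0 | 0 | 104 |
| 7 days before | 0 | 0 | 13 | 0 | 104 |
| 1 day before | 0 | 0 | 91 | 15 | 104 |
| Visit day | 13 | 0 | 104 | 21 | 104 |
| 7 days after | 104 | 21 | 104 | 76 | 104 |
| 14 days after | 104 | 76 | 104 | 104 | 104 |

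These are counts of date combinations, not expected proportions of patients. The result turns on three things: when dosing stops, whether 7 days are allowed, and whether one sample or both are tested. The SAP leaves the last open and contradicts itself on the second.

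**The case against.** The best defence is that 7 days was always meant. Within the Table 3-4 note, the primary-analysis sentence refers to double-blind drug and the secondary-analysis sentence changes to any study drug, which SAP 3.7.2 elsewhere explains as double-blind drug or open-label filgotinib. That change does nothing if no open-label man can reach the second branch. The Day 8 start of Table 3-5 fits the same intention. This stands as evidence of intent, but the operative sentence still says something else, and two programmers could build different datasets from it.

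A reader might infer that all Week 156 and Early Termination pairs on filgotinib are lost and none on Standard of Care. The documents do not support that. They do not say that open-label drug stops before or at Week 156 sampling. The one explicit rule, for the double-blind phase (Protocol 6.4), continues blinded drug until the Week 13 assessments are complete. A pair begun on or before the last dose can survive if the first sample decides.

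A reader might also infer that a decrease found at withdrawal would send the man to Monitoring. Protocol 3.7.3 and 6.7 say otherwise: he has an Early Termination visit and a safety follow-up, and leaves the study. Nor would a Week 156 decrease disappear from the report, because men who enter Monitoring are in the reversibility summaries and a by-subject listing.

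Finally, the table is for on-treatment data, so excluding samples taken well after stopping is legitimate. Early Termination semen is not collected at all if samples were taken within the previous 2 weeks (Protocol Appendix 2).

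**Conclusion.** The concern holds as a conflict in the SAP with a possible differential loss of data. It does not hold as a settled no-grace rule. Read literally, the Table 3-4 note contradicts the notes to Tables 3-2 and 3-3 and leaves follow-up Days 1 to 7 in neither semen table. End-of-phase pairs can then be excluded when open-label dosing stops on or before the visit day.

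The scope is narrow:
- Only the filgotinib-to-open-label-filgotinib sequence is exposed. The filgotinib-to-Standard-of-Care sequence follows the Standard of Care rule.
- Before Week 156, a pair that meets a decrease threshold normally precedes the last dose, because drug is stopped on its result.
- The displays concerned are descriptive, with no between-group estimate planned in SAP 6.5. The Week 13 primary analysis has its own cut-off.

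The documents do not allow an estimate of how many men are affected. For a visit-day last dose, the literal rule keeps 13 or 0 of 104 combinations and the 7-day rule keeps 104 or 21, depending on whether the first sample or both are tested. These counts assume a first sample 0 to 7 days after the visit. The text of SAP 3.1.2 (the semen analysis sets) was not available for this check. If it states a cut-off, that must be reconciled too.

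**What to change.** Change the secondary-analysis sentence in the Table 3-4 note as follows:
1. Limit the first branch to Standard of Care, and use the last dose of any study drug plus 7 days for open-label filgotinib, as in Tables 3-2 and 3-3.
2. Test each pair against the cut-off by its first evaluable sample, in line with SAP 3.7.3, and always keep the second sample of an included pair.
3. List, by sequence, any end-of-phase pairs still excluded, such as Early Termination pairs begun more than 7 days after the last dose. The 7-day rule does not rescue these, so some asymmetry with Standard of Care remains and should be visible.

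The cost is a reworded note and one listing. SAP Section 1 says that changes after finalization go in the clinical study report, so the clarification should be recorded there. The downside is that a few second samples would be taken up to about three weeks after the last dose (7 + 14 = 21 days), or later where a replacement third sample was approved (7 + 14 + 14 = 35 days at most).
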